- All participants will be adults (age 18 to 50), thus issues regarding assent from minors are not relevant.

7) Procedures involved in the Human Research

General Procedure: Over a 4-year period, 108 participants between the ages of 18 and 50 will be recruited to participate (to reach a final n of 90 subjects, assuming 20% attrition). Participants will comprise active duty, Reserve, National Guard, or recently discharged combat-exposed military personnel or DoD contractors from Operation Enduring Freedom/Operation Iraqi Freedom (OEF/OIF) meeting DSM-V diagnostic criteria for PTSD, in addition to some non-military individuals who meet the DSM-V diagnostic criteria for PTSD. Combat-exposed individuals within 10 years of return from OIF/OEF will be eligible. An age range of 18-50 years has been selected to minimize possible developmental and degenerative effects that could be expected in younger and older subjects and to encompass the age range of the majority of military personnel.

FORM: Application for Human Research
NUMBER
FORM DATE
PAGE

F200

02/2014

23 of 44

724 Prior to data analysis, subjects who consent will have a follow-up phone call where they will be
 725 administered the PCL-5, PHQ-9, and be asked about general sleep problems using the ESS and ISI.
 726

727 The procedures will essentially be identical to those used successfully in our pilot study of patients
 728 with mTBI. Participants will attend three laboratory sessions (see Figure 10 below). Visit 1 involves
 729 informed consent, demographic data collection, and basic psychiatric assessment. Participants will be
 730 provided with a wrist actigraph sleep monitor. After a week of at home monitoring, each participant will
 731 return for Visit 2, which is involves comprehensive neurocognitive assessment, neuroimaging, fear
 732 conditioning testing, objective sleepiness monitoring and heart rate monitoring. Then participants will be
 733 randomly assigned to one of two light therapy conditions (n = 45 per group) differing only in the
 734 wavelength emitted by each light therapy device. Participants will be randomly assigned to either the BL
 735 condition or the PL condition, using computerized permuted block randomization to match groups by
 736 gender. Participants assigned to the active treatment condition will undergo 6-weeks of at-home treatment
 737 with a light device fitted with blue light (BL) diodes, while those assigned to the Placebo (PL) condition

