At the conclusion of Visit 2, participants will be randomly assigned to either the BL condition or the PL condition, using computerized permuted block randomization to match groups by gender. All participants will be given a goLITE® unit to take home and provided with detailed training and instruction on its use. Depending on the light condition assigned, the goLITE will include either blue or amber LEDs. The goLITE BLU is commercially available and has a narrow bandwidth, peaking at $\lambda = 469$ nm, at 214 Lux, and panel irradiance $\text{mW/cm}^2 = 1.23$ at 20 cm. A similar appearing amber LED system (goLITE AMBER) will be employed for the PL devices, but will peak at $\lambda = 578$ nm, at 188 Lux, and total irradiance $(\text{mW/cm}^2) = 0.35$. Both of these devices have undergone extensive ocular safety testing (Sliney, 2009) and have been used successfully without incident in our prior study. Each participant will be instructed to use the unit each morning (within 2 hours of awakening and prior to 10:30 am) for 30 minutes per day over the next 6 weeks. Participants are permitted to engage in sedentary activities (e.g., read, watch TV, surf the internet, eat, engage in daily hygiene) while the unit is activated, as long as the light is within arm's reach and projecting to the eyes from within a 45-degree angle to either side (see Figure 14). A wattage use meter will be connected to the goLITE device to measure participant compliance in terms of duration, timing, and intensity of light exposure. They will be asked to record this via the Sleep Diaries A & B. This same procedure has been used in our prior work and has been well tolerated by participants, allowing them considerable flexibility to choose whether to use the light immediately upon arising, or after morning hygiene, meals, drive, etc., but while still ensuring that all treatment occur in the morning hours.

Safety and efficacy of the device itself is not being tested, rather, the effects of specific wavelengths of light on human performance; the device is simply used as a convenient method to deliver the light in a controlled and reliable way in order to assure the scientific validity of the results.

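### The conditions are said to differ only in wavelength, but the plan's own device figures also differ in light output, so a blue-amber difference cannot be credited to wavelength alone

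*Combined protocol and SAP*

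**What the plan says.** Section 7 (Procedures), General Procedure, describes participants as "randomly assigned to one of two light therapy conditions (n = 45 per group) differing only in the" "wavelength emitted by each light therapy device". Two other places say much the same. The Background, at the end of the light-therapy subsection, calls the placebo device identical apart from its amber diodes, and the General Procedure calls the placebo regimen identical treatment.

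The device specification is in the section on the at-home six-week treatment. The blue device peaks at 469 "nm, at 214 Lux, and panel irradiance" of 1.23 mW/cm² at 20 cm. The amber device peaks at 578 "nm, at 188 Lux, and total irradiance" of 0.35 mW/cm², with no distance. The same section sets out the purpose: "Safety and efficacy of the device itself is not being tested, rather, the effects of specific wavelengths of light on human performance".

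The documents do not say that the devices were matched on irradiance, photons or lux, do not explain the difference in output, and do not limit the wavelength conclusion. The only light covariate mentioned, under Actigraphic Sleep Measurement, concerns light from other daily sources.

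**The concern.** A two-arm trial can attribute an effect to one feature of the treatment only if the arms are alike in every other relevant feature. Here the plan says they are, and then prints output figures that are not alike. All participants on blue get one wavelength with one output, and all participants on amber get the other pair. Wavelength and output are therefore completely aliased with arm. No covariate can separate them, and adjusting for other daily light does not touch the problem.

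The Background gives light intensity a role of its own. It describes melatonin suppression by bright white light, says blue light achieves similar suppression at lower intensity, and cites antidepressant trials that used dim light as the placebo. A reader who follows the plan as worded would credit any advantage of blue to its wavelength, when output could account for some or all of it.

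**Working it through.** The plan states no output ratio, so there is no figure of its own to reproduce. All inputs come from the at-home treatment section.

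| | Blue | Amber |
|---|---|---|
| Peak wavelength | 469 nm | 578 nm |
| Illuminance | 214 lux | 188 lux |
| Irradiance | 1.23 mW/cm² | 0.35 mW/cm² |
| Label | panel | total |
| Distance | 20 cm | not given |

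**Ratios as printed (blue/amber)**

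- Irradiance: 1.23 / 0.35 = 3.51. Allowing for rounding of the inputs, the range is 1.225 / 0.355 = 3.45 to 1.235 / 0.345 = 3.58.
- Photons, treating each device as emitting only at its peak, so that photon number is proportional to irradiance times wavelength: (1.23 × 469) / (0.35 × 578) = 576.87 / 202.3 = 2.85.
- Lux: 214 / 188 = 1.14. Put the other way, amber is 1 − 188/214 = 12% lower.

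Blue is higher on all three.

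**How far the irradiance ratio depends on the missing distance.** Assume an inverse-square law and suppose the amber figure was read at d cm. Its value at 20 cm would be 0.35 × (d/20)², and the irradiance ratio at 20 cm would be 1.23 / [0.35 × (d/20)²].

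| Assumed amber distance | Irradiance ratio at 20 cm |
|---|---|
| 10 cm | 14.1 |
| 20 cm | 3.5 |
| 30 cm | 1.6 |
| 37.5 cm | 1.0 |
| 40 cm | 0.88 |

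The ratio equals 1 at d = 20 × √3.514 = 37.5 cm. The inverse-square law and these distances are assumptions, used only to show the range.

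**Would a different distance rescue the claim?** Not on every metric. At 37.5 cm, where irradiance is equal, the photon ratio is 469 / 578 = 0.81. Equal irradiance and equal photons cannot both hold for two different wavelengths. Whether the arms are alike in output therefore depends on the metric chosen, and the plan names none.

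**Lux and irradiance.** The printed figures give 214 / 1.23 = 174 lux per mW/cm² for blue and 188 / 0.35 = 537 for amber. Similar lux does not mean similar energy.

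**The case against.** The strongest reply has four parts.

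*The 3.5 is not established.* The two irradiances carry different labels, only one has a distance, and participants use the device within arm's reach, for which no irradiance is given. This stands. A reader might infer that people on blue received 3.5 times the light energy at the eye. The documents do not support that: 3.5 is the ratio of the printed figures and becomes a ratio of delivered light only under a common distance. The uncertainty does not rescue the claim of a sole difference, though. Either the outputs differ, or the comparator has not been described well enough to say.

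*The devices are close in brightness, and unequal energy follows from unequal colour.* This stands in part. With lux only 12% lower, calling amber the dimmer device would be too strong. Since lux is weighted by wavelength, rough lux matching leaves an energy gap, and irradiance is not self-evidently the right standard. But the plan never says it matched on lux, and lux is not equal either.

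*The analysis is already blue against placebo.* This also stands. The hypotheses under Specific Aims and the between-group factor under Data Analysis are worded as the two light conditions, and the sentence about wavelengths sits in the device description. But the section on potential benefits also promises information on the effects of short-wavelength light, so wavelength wording appears where conclusions are drawn.

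*The figures are disclosed.* They are, but disclosure does not correct the statement they contradict.

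**Conclusion.** The concern holds as a limit on interpretation. On the plan's own figures the two conditions differ in output as well as wavelength: 3.5-fold in irradiance and about 2.9-fold in photons if both irradiances refer to the same distance, and 1.14-fold in lux as printed. The photon figure also treats each device as emitting at its peak. A difference between arms can be attributed to the blue device as supplied, compared with the amber device as supplied, and not to wavelength alone.

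A reader might go further and infer that the efficacy comparison is biased or the trial invalid. That does not follow. Randomisation protects the contrast between the two devices whatever their outputs, and the planned analyses, sample size and power are unaffected.

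**What to change.** - Bring the Background and the General Procedure into line with the device figures. Remove the statement that wavelength is the sole difference, and qualify the two descriptions of the placebo as identical.
- State the permitted conclusion as the blue device against the amber device, each as supplied, and align the purpose statement in the at-home treatment section ("rather, the effects of specific wavelengths of light on human performance") with it.
- Report output for both devices on the same metric and at the same distance, and say which metric, if any, was used to match them.

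No change to either device's output or use is proposed, and which figures are right is for the sponsor to reconcile. The cost is a slightly narrower claim and a measurement of both devices on a common basis.

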**FORM: Application for Human Research**

| NUMBER | FORM DATE | PAGE |
|--------|-----------|----------|
| F200 | 02/2014 | 24 of 44 |

758 exclusion from the study. The Rivermead Post-Concussive Symptoms Questionnaire (RPCSQ) will be
759 administered to confirm that any participants who may have experienced concussion during their
760 traumatic event did not lose consciousness or experience post-traumatic amnesia. Research Technicians
761 who have been trained and meet predetermined qualifications to administer a Structured Clinical
762 Interview by doctoral level clinical psychologists with training and experience with these instruments will
763 administer the SCID. All SCID administrations will be reviewed via supervision by a qualified doctoral
764 level clinical psychologist immediately following the participant's interview. Female participants will
765 also provide information about their menstrual cycle (length of cycle and time since last menses) because
766 this is critical in the interpretation of brain metabolite levels during magnetic resonance spectroscopic
767 imaging. We do not know if MRI scanning presents a risk to unborn fetuses, so we will ask all female
768 participants of childbearing potential to complete a urine pregnancy test immediately prior to the scan.
769 Female participants must have a negative pregnancy test before the MRI scan can be initiated. This
770 pregnancy test will be performed in the Department of Psychiatry. All subjects will wear a heart rate
771 monitor for the duration of this visit. Selection criteria for all subjects are as follows:

772 During Visit 1, participants will be fitted with a wrist-worn actigraph to monitor sleep/wake
773 patterns. This device will also log exposure to light in three wavelengths (red, green, blue) to measure
774 compliance with the protocol. Participants will also be introduced to the online sleep diary collection
775 system and will be given an automated email each morning reminding them to log in and complete the
776 sleep diary.

777 **Visits 2 and 3: Assessment/Scanning Visits:** One week after Visit 1, participants will return for
778 Visit 2. Participants will complete a detailed demographic (Day of Scan Questionnaire (DSIQ)) and health
779 questionnaire and will be fitted for a heart rate monitor to be worn for the duration of the visit, save for
780 the MRI scan where heart rate will be measured by MRI safe leads as part of the MRI scanner. Subjects
781 will complete a comprehensive baseline assessment of neurocognitive and emotional functioning, coping
782 capacity, and resilience. Participants will also undergo a validated *de novo* fear conditioning and
783 extinction procedure [98-101], and a series of functional neuroimaging and neurochemistry scans.
784 Additionally, participants will complete subjective and objective measures of sleepiness and alertness
785 throughout the day. The following specific tasks and procedures will be administered during the
786 assessment session:

787 **Emotional Functioning/Coping/Symptom Severity:** PTSD severity will be assessed using the
788 20-item National Center for PTSD Checklist, Military Version (PCL-5), Patient Health Questionnaire
789 (PHQ-9), and Clinician Administered PTSD Scale-5 (CAPS-5). Further assessment of psychopathology
790 will be made via administration of the Beck Depression Inventory (BDI-II); Beck Anxiety Inventory
791 (BAI); and Spielberger State-Trait Anxiety Inventory (STA). Participants will also complete measures
792 of resilience (Connor-Davidson Resilience Scale (CD-RISC)), Evaluation of Risks (EVAR), the Satisfaction
793 with Life Scale (SWLS) and the Gratitude Questionnaire (GQ6). The Balloon Analogue Risk Test
794 (BART) will be done to measure risk taking.

795 **Subjective Sleep Measures:** To assess general sleep quality, daytime sleepiness, and
796 parasomnias, participants will complete the Pittsburgh Sleep Quality Index (PSQI)[102], the Epworth
797 Sleepiness Scale (ESS) [103], the Insomnia Severity Index (ISI)[104], and the Disturbing Dream and
798 Nightmare Severity Index (DDNSI) [22]. The Stanford Sleepiness Scale (SSS) [105] will be completed at

FORM: Application for Human Research

[figure not shown]
| NUMBER | FORM DATE | PAGE |
|--------|-----------|----------|
| F200 | 02/2014 | 25 of 44 |

799 three times during the assessment day. The Functional Outcome of Sleep Questionnaire (FOSQ) and
 800 Sleep Diaries A & B will also be done.

801 **Neurocognitive Assessment:** All participants will complete a comprehensive neurocognitive
 802 assessment battery to include:

803 1. Repeatable Battery for the Assessment of Neuropsychological Status (RBANS). The
 804 RBANS is a brief battery of well-normed neuropsychological tests with two alternate forms (RBANS A
 805 and RBANS B) to permit repeated testing. The test provides several index scores, including: Total Score,
 806 Immediate Memory, Visuospatial/Constructional, Language, Attention, and Delayed Memory. This brief
 807 battery will be administered to assess change in cognitive performance in each group following treatment.
 808 Subject responses will be recorded via recording device for the Semantic Fluency portion of the RBANS
 809 assessment in order to ensure that their complete responses are captured given that they may respond
 810 faster than the study team may otherwise be able to record. No identifiers will be used and these recording
 811 will be assigned to the subject ID number only. Recordings will be listened to the same day they are
 812 created and compared to the initial response collection to ensure the study team captured the subject's
 813 complete response, anything missed will be transcribed onto the RBANS form. The recording will then be
 814 deleted.

815 2. Fear Conditioning Paradigm. Our group has developed a fear-conditioning/fear extinction
 816 paradigm that is highly effective at discriminating individuals with PTSD from healthy controls [98-101].
 817 The protocol consists of 4 experimental phases: Habituation, Conditioning, Extinction and Extinction
 818 Recall. Subjects first choose a level of mild
 819 electric shock that is "highly annoying but not
 820 painful" while being administered shocks of
 821 increasing intensities through electrodes
 822 connected to two fingers. For this paradigm, the
 823 conditioned stimuli (CSs) consist of digital
 824 photographs of three differently colored vehicles
 825 (blue, red or yellow) displayed on a computer
 826 screen within the image of two different
 827 photographic environments (contexts), a
 828 "conditioning context" in which the
 829 unconditioned (shock) stimulus (US)
 830 accompanies certain CSs (CS+s) during
 831 Conditioning and an "extinction context" in
 832 which CS+s occur without USs during the Extinction and Extinction Recall phases. Before each
 833 experimental phase except Habituation, subjects are told they "may or may not be shocked." During
 834 Conditioning, 16 CS+'s (8 each of 2 different colors) are presented in the conditioning context and a 0.5-
 835 sec US (shock) immediately follows the offset of 10 of 16 CS+ presentations (5 of the 8 of each CS+
 836 color). Sixteen randomly interspersed presentations of the third vehicle color (CS-s) are never paired with
 837 the US. During the Extinction phase, one CS+ color (CS+E) appears 16 times in the extinction context,
 838 along with 16 interspersed CS-s and no USs. The other CS+ color (CS+U) does not appear and therefore
 839 remains un-extinguished. During the Extinction Recall phase, the 8 CS+Es and 8 CS+Us are presented in
 840 the extinction context with 16 interspersed CS-s and no USs. The measurement of conditioned fear is

**FORM: Application for Human Research**

| NUMBER | FORM DATE | PAGE |
|--------|-----------|----------|
| F200 | 02/2014 | 26 of 44 |

841 palm-recorded skin conductance response (SCR), a reliable index of sympathetic activation. Participants
842 will be conditioned and undergo extinction prior to entry into the scanner. During scanning, participants
843 will again be confronted with the previously extinguished stimuli to evaluate extinction recall, a hallmark
844 deficit of PTSD. It is expected that improved sleep due to the BL condition will lead to improved
845 generalization of the extinction response and extinction recall.

846 **Modified Sleep Latency Test (MSLT):** Participants will undergo 3 MSLT procedures with
847 polysomnographic (PSG) recording over the course of the assessment day. A trained technician will fit
848 each participant with a standard electrode montage for PSG recording. Standard PSG will be recorded
849 using the Polysmith 11.0 system that is installed in our sleep laboratory facilities. During each MSLT, the
850 participant will be given up to 20 minutes to fall asleep in a private, darkened, sound-attenuated bedroom.
851 PSG recordings will be scored by a trained technician to determine the latency to fall sleep. The mean
852 latency to sleep is taken as an indication of objective sleepiness.

853 **Psychomotor Vigilance Test (PVT):** The PVT is a 10-minute computerized measure of
854 sustained attention and psychomotor vigilance that has been shown to be exquisitely sensitive to sleep
855 deprivation. The PVT currently serves as the “gold standard” for assessing degradation in alertness and
856 vigilance following sleep loss.

857 **Functional Neuroimaging:** Subjects will be screened for any contraindications to MRI and magnetic
858 materials. The investigator or MRI Technologist will explain the MRI system and the scan that they are
859 about to take part in. The subject will be asked to lie down on the scanner bed. Some part of the subject's
860 body may be covered or enclosed within an FDA or UA HSPP approved MRI coil. The subject may be
861 asked to interact with a peripheral system such as a button, joystick, or TV system before, during, or after
862 the scan.

863 Blood Oxygen Level Dependent (BOLD) functional magnetic resonance imaging (fMRI) will
864 be collected at the University of Arizona Translational Bioimaging Resource. The MRI hardware and
865 procedures immediately to follow are approved by the FDA. A Siemens Skyra 3T whole body high-speed
866 imaging device equipped for echo planar imaging (EPI) (Siemens Medical Systems, Iselin, NJ) will be
867 used. Head movement will be restricted using expandable foam cushions. After an automated scout
868 image is acquired and shimming procedures performed to optimize field homogeneity, high-resolution 3D
869 MPRAGE sequences (TR/TE/flip angle=7.25ms/3ms/7°) with an in-plane resolution of 1.3 mm, and 1
870 mm slice thickness, will be collected for spatial normalization, positioning the slice prescription, and for
871 subsequent morphometric analysis. Then a T1-weighted (TR/TE/flip angle=8sec/39msec/90°) and a T2-
872 weighted (TR/TE/flip angle=10sec/48ms/120°) sequence will be used to gather sets of images to assist in
873 registration of the functional data to the high-resolution anatomical scan. Functional MRI images (blood
874 oxygenation level dependent or BOLD; Kwong et al 1992) will be acquired using a gradient echo T2*-
875 weighted sequence (TR/TE/flip angle=2 sec/40msec/90°). Prior to each scan, four images are acquired
876 and discarded to allow longitudinal magnetization to reach equilibrium. The T1, T2, and gradient-echo
877 functional images will be collected in the same plane (whole brain acquisition; axonal slices angled
878 perpendicular to the AC-PC line) with the same slice thickness (3.125 mm, skip 1mm; voxel size 3.125 x
879 3.125 x 3.125 mm), excitation order (descending) and phase encoding (head-to-foot). During fMRI,
880 participants will complete four functional tasks:

FORM: Application for Human Research

| NUMBER | FORM DATE | PAGE |
|--------|-----------|----------|
| F200 | 02/2014 | 27 of 44 |

881 1. Masked Affect Task (MAT): This task, first developed by our group back in the mid-1990's
 882 [110], presents a series of facial expressions displaying happiness or fear, each for only 16 msec and
 883 masked immediately by a neutral image from a different poser for 184 msec (Figure 14). At this rate of
 884 presentation, the "masked" affective expression is not consciously perceived, yet is still processed via an
 885 extrastriate pathway to the amygdala that bypasses normal cortical processing. This task has been shown
 886 to selectively activate the amygdala in healthy participants. Moreover, in our laboratory, exaggerated
 887 amygdala response has been found on this task in patients with PTSD [27]. Our laboratory has extensive
 888 experience using this task with patients with PTSD and anxiety disorders [27, 111-115], and healthy
 889 adults and children [116-118].

890 2. Extinction Recall (ER): This task measures the
 891 retention of the extinction memory established during the
 892 previous fear conditioning session. While undergoing fMRI,
 893 participants will view the previously conditioned images from
 894 the Fear Conditioning and Extinction Task. Here, 8 CS+E, 8
 895 CS+U, and 16 CS- trials will be presented (without any
 896 shocks). Skin conductance responses will also be collected
 897 while participants are undergoing the scan. During this task,
 898 the contrast of interest will be CS+E vs. CS+U, permitting the
 899 isolation of psychophysiological and brain responses that are
 900 specific to extinction recall.

901 3. Resting State Scan (RS): Emerging evidence suggests
 902 that the brain shows stable patterns of functional connectivity
 903 during the resting state and that these patterns may be
 904 particularly useful in elucidating specific networks [119-122].
 905 Therefore, in addition to the probe tasks described above subjects will also be scanned for 10 minutes
 906 with eyes closed and instructed to let their "mind wander." Functional connectivity will be evaluated
 907 from pre- to post-treatment for the two conditions.

908 4. Anticipation Task: The Emotional Anticipation Task was adapted on the basis of Aupperle et al.'s
 909 (2013) study design and lasts a total of 7 min and 8 seconds. Two version of the anticipation tasks will be
 910 used, in order to have two different versions of the tasks for the baseline and follow up visit. Participants
 911 are presented with a grey background with a black arrow alternating randomly in its direction from left to
 912 right (Baseline). Participants are instructed to indicate via button press which direction the arrow was
 913 pointing in. Participants are told that when the screen turns yellow, a negative picture will soon appear
 914 (Negative Anticipation (NA)). If the screen turns blue, a positive picture will soon appear (Positive
 915 Anticipation (PA)), and if the screen turns green a positive *or* a negative picture will soon appear
 916 (Uncertain Anticipation (UA)). The picture stimuli consist of positive and negative pictures from the
 917 International Affective Picture System (IAPS). The most unpleasant (e.g., mutilated bodies) as well as the
 918 most pleasant (e.g., animals) pictures were chosen from the picture set. The aim of this task is to
 919 investigate whether the intervention changes neural responses during anticipation of negative stimuli.

[figure not shown]

Figure 14. Masked Affect Task: A target emotional facial expression is presented for 16 ms and masked immediately by a neutral face for a longer duration (184 ms). This effectively prevents awareness of the target emotional expression, although it is perceived at a non-conscious level.

| NUMBER | FORM DATE | PAGE |
|--------|-----------|----------|
| F200 | 02/2014 | 28 of 44 |

Spectroscopic Neuroimaging: While all MRI

hardware used during this study is FDA-approved, as part of the MRI session, one MRI sequence will be conducted that uses investigational software that enables collection of unique spectroscopic data. This scan, referred to as the MEGA-PRESS sequence, uses Proton Magnetic Resonance Spectroscopy (MRS) to measure chemicals in the brain, specifically, cerebral metabolites and neurotransmitter concentrations. It is very similar to other FDA-approved MRS sequences, but it does a better job at quantifying certain metabolites, namely, GABA. Per the Master Research Agreement (MRA) between Siemens and the University of Arizona, as a Works in Progress (WIP), the MEGA-PRESS sequence complies with all FDA guidelines for magnetic resonance imaging (<https://www.fda.gov/regulatory-information/search-fda-guidance-documents/criteria-significant-risk-investigations-magnetic-resonance-diagnostic-devices-guidance-industry-and>) and is suitable for testing in a clinical

environment. Because of this, the MEGA-PRESS sequences does not increase the risk to subjects.

A key element of the proposed project involves assessment of changes in brain neurochemistry as a function of 6-weeks of light therapy treatment and associated changes in sleep quality. Growing evidence suggests that some of the deficits in memory and emotional regulation that occur for patients with PTSD are related to alterations in neurochemistry within key regions of the hippocampus and ACC (Karl & Werner, 2010). In particular, patients with PTSD show decreased NAA in the hippocampus and ACC, as well as reduced concentrations of choline in the hippocampus and increased levels in the ACC. These are often compared directly as ratios relative to creatine (Cr). Assuming that improved sleep leads to improvement in emotional functioning, this will permit us to identify a potential mechanism for this improvement. Presently, for ¹H MRS imaging, two voxels will be placed, one encompassing the dorsal anterior cingulate cortex just anterior to the genu of the corpus callosum and another placed at the amygdala-hippocampal complex within the mesial temporal lobe (see figure 15). All ¹H MRS measurements will be performed using a Siemens TIM Trio 3T whole body high-speed imaging device (Siemens Medical Systems, Iselin, NJ) and a 32-channel single-tuned (170.3 MHz) "birdcage" coil for radiofrequency (RF) transmission and signal reception, both of which are approved by the FDA. The following brain metabolites will be collected and analyzed: alanine (Ala), aspartate (Asp), choline (Cho), Gamma Amino Butyric Acid (GABA), Glutamate (Glu), Glutamine (Gln), glutathione (GSH), glycine (Gly), myo-I, N-acetylaspartate (NAA), N-acetylaspartylglutamate (NAAG), creatine (Cr), phosphocreatine (PCr), scyllo-inositol (Scy), taurine (Tau) and lactate (Lac).

[figure not shown]

Figure 15. MRS Spectroscopy: Placement of voxels within the dorsal ACC and left hippocampus.

FORM: Application for Human Research

| NUMBER | FORM DATE | PAGE |
|--------|-----------|----------|
| F200 | 02/2014 | 29 of 44 |

At Home Six-Week Light Exposure Treatment:

At the conclusion of Visit 2, participants will be randomly assigned to either the BL condition or the PL condition, using computerized permuted block randomization to match groups by gender. All participants will be given a goLITE® unit to take home and provided with detailed training and instruction on its use. Depending on the light condition assigned, the goLITE will include either blue or amber LEDs. The goLITE BLU is commercially available and has a narrow bandwidth, peaking at $\lambda = 469$ nm, at 214 Lux, and panel irradiance $\text{mW/cm}^2 = 1.23$ at 20 cm. A similar appearing amber LED system (goLITE AMBER) will be employed for the PL devices, but will peak at $\lambda = 578$ nm, at 188 Lux, and total irradiance $(\text{mW/cm}^2) = 0.35$. Both of these devices have undergone extensive ocular safety testing (Sliney, 2009) and have been used successfully without incident in our prior study. Each participant will be instructed to use the unit each morning (within 2 hours of awakening and prior to 10:30 am) for 30 minutes per day over the next 6 weeks. Participants are permitted to engage in sedentary activities (e.g., read, watch TV, surf the internet, eat, engage in daily hygiene) while the unit is activated, as long as the light is within arm's reach and projecting to the eyes from within a 45-degree angle to either side (see Figure 14). A wattage use meter will be connected to the goLITE device to measure participant compliance in terms of duration, timing, and intensity of light exposure. They will be asked to record this via the Sleep Diaries A & B. This same procedure has been used in our prior work and has been well tolerated by participants, allowing them considerable flexibility to choose whether to use the light immediately upon arising, or after morning hygiene, meals, drive, etc., but while still ensuring that all treatment occur in the morning hours.

Safety and efficacy of the device itself is not being tested, rather, the effects of specific wavelengths of light on human performance; the device is simply used as a convenient method to deliver the light in a controlled and reliable way in order to assure the scientific validity of the results.

Actigraphic Sleep Measurement: Daily sleep, activity, and light exposure will be collected via the Respiromics Actiwatch Spectrum®. This actigraphic wrist-watch device uses a built-in accelerometer to unobtrusively measure and record ambulatory activity levels and sleep 24 hours a day. This data can then be analyzed via sleep analysis software (Actiware 5®) that includes algorithms that transform activity data into probable sleep periods. The Actiwatch Spectrum also includes three-color light sensors that provide irradiance and luminous lux recordings in three-color bands of the visible spectrum, including red, green, and blue (Figure 17). The light sensor will be used to verify that subjects are in fact undergoing the daily light treatment and will permit covariation of other daily light sources in the statistical analyses. The device also records periods of off-wrist time to determine compliance. Data

[figure not shown]

Figure 16. Participants will maintain the device at arms length within the peripheral vision for 30 minutes each morning.

[figure not shown]

Figure 17. Actiwatch Spectrum and Actigram: The device collects wrist activity data (black bars) that are translated into sleep/wake periods (white/red bars at bottom of graph), as well as minute by minute light exposure (yellow = total light; blue = blue light; green = green light; red = red light).

FORM: Application for Human Research

| NUMBER | FORM DATE | PAGE |
|--------|-----------|----------|
| F200 | 02/2014 | 30 of 44 |

997 will be scored by the Actiware 5® program, checked for validity, and summary indices of total sleep time,
 998 sleep efficiency, sleep onset latency, wake after sleep onset (WASO), and fragmentation index will be
 999 calculated for each day and averaged across the study period.

1000 **Compliance Monitoring:** Compliance with the study requirements will be monitored in
 1001 several ways. First, participants are required to log into the internet each day to complete the sleep diary
 1002 and report timing of light usage. This is an effective means for monitoring general compliance. On-line
 1003 compliance will be monitored, and participants will be contacted by phone and/or email if they have not
 1004 logged in for more than 48 hours. Second, use of the lights will be monitored by a recording device built
 1005 into the light device that records a time stamp each time the light is engaged. Third, participants are
 1006 required to wear the wrist actigraph at all times. This device includes a light monitor that is sensitive to
 1007 various wavelengths of light. This light data will be evaluated at the conclusion of the study to identify
 1008 whether there is a detectable change in blue/red light during the period of reported light exposure.

1009 **Post-Treatment Assessment and Scan:** At the completion of 6-weeks of BL or PL, participants
 1010 will return to the imaging center for Visit 3 to complete an
 1011 identical series of assessment and neuroimaging tasks as in
 1012 Visit 2, as well as a repeated administration of the CAPS.
 1013 Participants will return wrist actigraphs and the goLITE
 1014 device.

1015 Please note that subjects will be offered and required
 1016 to wear earplugs and/or earphones to minimize the scanner
 1017 noise. Subjects will be able to converse with a staff member
 1018 via a microphone and speaker system at all times during the
 1019 scanning session. Subjects will be provided with an
 1020 emergency button to indicate an immediate concern.
 1021 Subjects may ask to have a scan stopped and discontinue
 1022 participation in the study at any time.

1023 **Follow-Up.** After subjects complete the study, prior
 1024 to data analysis, subjects will be sent an email (*Follow-up*
 1025 *Script.doc*) with a link to an online ICF Addendum
 1026 (*PTSD_ICF_addendum.doc*) and, if they agree, subjects
 1027 will complete a 10- to 15-minute follow-up online survey,
 1028 where they will be administered the PCL-5, PHQ-9, and be
 1029 asked about general sleep problems using the ESS and ISI.
 1030 If subjects cannot complete this follow-up online, follow-up
 1031 assessments will be administered over the phone.

D. DATA ANALYSIS

1034 **Global Statistical Analysis Approach:** Behavioral
 1035 data from the neurocognitive, sleep, and symptom measures
 1036 will be evaluated for clinical severity and transformed into change metrics from baseline to post-treatment
 1037 sessions. Baseline characteristics between subject groups will be examined using analysis of variance
 1038 (ANOVA) and chi-square tests, as appropriate, and randomization will be stratified by severity of PTSD

[figure not shown]

Figure 18. Power analyses show that the proposed sample size should be adequate to address the primary hypotheses.

